4.4.3. Missed and Virtual Visits due to Disaster or Public Health Emergency

A by-participant listing of participants with missed or virtual visits due to COVID-19 will be provided by participant ID number in ascending order.

Information regarding missed or virtual visits due to COVID-19 will be collected as free text in the CRF comment fields. The determination of missed or virtual visits due to COVID-19 will be done using Natural Language Processing (NLP) to search the CRF comment fields. A detailed explanation of the algorithm is given in [Appendix 2](#).

4.4.4. Adverse Events Due to Disaster or Public Health Emergency

AEs of COVID-19 will be included in analyses of AEs if applicable, which will be determined through COVID-19 SMQ Narrow search. A by-participant listing of AEs of COVID-19 will be provided if applicable.

5. BASELINE CHARACTERISTICS

5.1. Demographics and Baseline Characteristics

Participant demographic variables (i.e., age, sex, race, and ethnicity) and baseline characteristics (body weight [in kg], height [in cm], body mass index [BMI; in kg/m²]) will be summarized using descriptive statistics for continuous variables and using number and percentage of participants for categorical variables. The summary of demographic data will be provided for the Safety Analysis Set.

A by-participant demographic listing, including the informed consent date, will be provided by participant ID number in ascending order.

5.2. Other Baseline Characteristics

Other baseline characteristics will be summarized:

- Baseline HIV-1 RNA (\log_{10} copies/mL)
- Baseline HIV-1 RNA categories (copies/mL) (a) < 50 and (b) \geq 50
- Baseline CD4+ T cell count (cells/ μ L)
- Baseline CD4+ T cell count categories (cells/ μ L): (a) < 50, (b) \geq 50 to < 200, (c) \geq 200 to < 350, (d) \geq 350 to < 500, and (e) \geq 500
- Baseline CD4+ T cell percentage (%)
- Baseline estimated glomerular filtration rate using Cockcroft-Gault formula eGFR_{CG} (mL/min)
- HIV disease status
- Mode of infection (HIV risk factors)
- Time from HIV diagnosis to ART initiation (in days)
- Duration of ART prior to study (in years)
- Fiebig Stage at ART Initiation
- CD4+ T cell count prior to start of initial ART (cells/ μ L)
- CD4+ T cell count categories prior to start of initial ART (cells/ μ L): (a) < 50, (b) \geq 50 to < 200, (c) \geq 200 to < 350, (d) \geq 350 to < 500, and (e) \geq 500

- HIV-1 RNA at HIV diagnosis (\log_{10} copies/mL)
- HIV-1 RNA categories at HIV diagnosis (copies/mL) (a) ≥ 50 to < 2000 , (b) ≥ 2000 to ≤ 5000 , (c) > 5000
- HIV-1 RNA prior to start of initial ART (\log_{10} copies/mL)
- HIV-1 RNA categories prior to start of initial ART (copies/mL): (a) ≥ 50 to < 2000 , (b) ≥ 2000 to ≤ 5000 , (c) > 5000

These baseline characteristics will be summarized using descriptive statistics for continuous variables and using number and percentage of participants for categorical variables. The summary of these baseline characteristics will be provided for the Safety Analysis Set. No formal statistical testing is planned.

A by-participant listing of other baseline characteristics will be provided by participant ID number in ascending order.

5.3. Medical History

General medical history data will be collected at screening and listed only. General medical history data will be coded using the current version of Medical Dictionary for Regulatory Activities (MedDRA).

6. EFFICACY ANALYSES

6.1. Definition of Efficacy Endpoints

Efficacy endpoints include the following:

- Time to virologic rebound following ATI based on 2 different cutoff values:
 - 1) ≥ 50 copies/mL
 - 2) ≥ 200 copies/mL
- Change in plasma viral load set-point following ATI
- Time to ART resumption following ATI

6.2. Statistical Hypotheses for Efficacy Endpoints

CCI

6.3. Analysis of Efficacy Endpoints

The Full Analysis Set will be used for the efficacy endpoint analysis.

Descriptive statistics will be provided for HIV-1 RNA data as follows:

- Baseline HIV-1 RNA value
- Change from baseline in HIV-1 RNA (\log_{10} copies) at each postbaseline visit up to the last exposure date for participants who have permanently discontinued study drug.

The baseline HIV-1 RNA value will be defined as the last measurement obtained on or prior to the date/time of first dose of study drug. Change from baseline to a postbaseline visit will be defined as the visit value minus the baseline value, and summarized using descriptive statistics (n, mean, SD, 95% confidence interval [CI], median, Q1, Q3, minimum, and maximum). The mean, median, Q1, Q3, minimum, and maximum values will be displayed to the reported number of digits; SD values will be displayed to the reported number of digits plus 1. In the case of multiple values in an analysis window, data will be selected for analysis as described in Section 3.8.3. No formal statistical testing is planned.

The change in plasma viral load set-point is defined as the value following ATI minus the pre-ART value. The plasma viral set-point following ATI is calculated as the geometric mean of all the HIV-1 RNA measurements between a specified start and end date. The start date and end date will be provided by the study's clinical development team and clinical virologist based on individual participant data review. The pre-ART set point value is the HIV-RNA load count prior to start of initial ARV treatment recorded in the clinical database. Change in plasma viral load set-point following ATI will be summarized and analyzed in the same fashion as that of the change from baseline in plasma \log_{10} HIV-1 RNA.

A by-participant listing for HIV-1 RNA value will be provided by participant ID number and visit in chronological order.

A figure of individual participant \log_{10} HIV-1 RNA value versus time following ATI will be provided.

Virologic rebound is defined as: at any visit a rebound in HIV-1 RNA to cutoff value, which is subsequently confirmed at the following scheduled or unscheduled visit.

Time to virologic rebound will be analyzed using the Kaplan-Meier method. Participants who do not rebound will be censored at the last HIV-1 RNA collection date during ATI period.

Time to ART resumption following ATI will be analyzed in the same fashion as that of the time to virologic rebound using the Kaplan-Meier method. Participants who do not resume ART will be censored at the last study date. Participants with ART resumed on or prior to end of Period 3 visit date will be flagged.

The above time-to-event endpoints are defined as the time interval (in weeks) between the ATI start date and the event or censoring date, calculated as $(\text{the event or censoring date} - \text{ATI start date} + 1) / 7$.

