- Plasma HIV-1 RNA measurements of \geq 1,000 copies/mL for 8 consecutive weeks AND no drop of $0.3 \log_{10}$ from the previous week
 - Once the first confirmed HIV-1 RNA value of \geq 50 copies/mL is detected, this will trigger weekly testing to monitor the HIV-1 RNA measurements,

OR

- Confirmed plasma HIV-1 RNA $>$ 100,000 copies/mL

OR

- If a confirmed CD4+ T cell count $<$ 350 cells/ μ L

OR

- If a participant becomes pregnant

OR

- ART may also be reinitiated during ATI per participant request, or at the discretion of the investigator, or sponsor due to other clinical criteria

Participants who restart ART in Period 4A will complete 6 study visits scheduled every 2 weeks over a 12-week period.

Participants who opt to remain off ART in Period 4B for the ATI extension will complete 6 study visits scheduled every 2 weeks over a 12-week period. If the participant's HIV-1 RNA remains at $<$ 50 copies/mL throughout Period 4B, additional procedures may be required at the end-of-study visit.

No study drug (VES, VRC07-523LS, or CAP256V2LS) will be administered in this period.

Table 6. Periods 4A and 4B Study Visits and Study Drug Administration

Periods 4A & 4B						
Week	49	51	53	55	57	59
Day	343	357	371	385	399	413
VES Dose	No dosing					
VRC07-523LS and CAP256V2LS Dose	No dosing					
4A: ART Restart 4B: ATI Extension Days 337 to 413						

VES = Vesatolimod, Every Period 4 study visit is based on the Day 0 visit + the number of postponement days required to confirm ATI eligibility in Period 1, if applicable

6.6.1. Treatment Assessments—Days 337 to 413

The following assessments are to be completed at every visit for Periods 4A and 4B, unless otherwise specified. All study visits are to be completed within \pm 3 days of the protocol-specified visit date (based on the Day 0 visit + the number of postponement days required to confirm ATI eligibility in Period 1, if applicable), and study procedures are to be completed within \pm 2 hours of the protocol-specified time point.

- Symptom-directed physical examination (**Day 343 and at each visit every 4 weeks thereafter**)
- Vital signs (blood pressure, pulse, respiration rate, oxygen saturation, and temperature) (**Day 343 and at each visit every 4 weeks thereafter**)
- Body weight (**Day 343 and at each visit every 4 weeks thereafter**)
- Obtain blood samples for:
 - Plasma HIV-1 RNA

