3.2. Participant Grouping

For analyses based on All Enrolled Analysis Set and FAS, participants will be grouped according to the treatment to which they were enrolled (i.e., VES + VRC + CAP). For analyses based on Safety Analysis Set, PK Analysis Set and Immunogenicity Analysis Set, participants will be grouped according to the actual treatment received.

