3.4. Examination of Participant Subgroups

There are no prespecified participant subgroupings for efficacy and safety analyses.

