3.8. Visit Definitions

3.8.1. Definition of Key Dates and Study Day

Study Days are calculated from the first dosing date of study drug and derived as follows:

- For postdose study days: Assessment Date – First Dosing Date + 1
- For days prior to the first dose: Assessment Date – First Dosing Date

Therefore, study day 1 is the day of first dose of study drug administration.

Baseline Value is defined as the last value obtained on or prior to the first dose of study drug.

Last Dose Date is defined as the latest dose date of any study drug as recorded on the Study Drug Administration eCRF (i.e., VES, VRC07-523LS, CAP256V2LS).

Last Study Date is the latest clinic visit date, and/or the laboratory visit dates, and/or latest AE onset date and end date, whichever is latest, including the any follow-up visit dates for participants who completed study.

Last Exposure Date is defined as last study date for all participants who receive VRC07-523LS and/or CAP256V2LS infusion. This date is defined considering the prolonged exposure of VRC07-523LS and CAP256V2LS after the last dose date through the end of study.

ATI Start Date is defined as the last stop date of Non-Study Antiretroviral (ARV) Medication between the study drug start and discontinuation, plus one day.

ART Restart Date is defined as the start date of resuming ART or compatible regimen after ATI start on Non-Study ARV Medication eCRF form.

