3.8.2. Analysis Visits

The nominal visit as recorded on the eCRF or lab date will be used when data are summarized by visit. Any data relating to unscheduled visits will not be assigned to a particular visit or time point and in general will not be included in by-visit summaries. However, the following exceptions will be made:

- An unscheduled visit prior to the first dose of study drug may be included in the calculation of baseline value, if applicable.
- Unscheduled visits after the first dose of study drug will be included in determining the maximum postbaseline toxicity grade and time to event analyses.
- For participants who prematurely discontinued from the study drug, early termination (ET) data will be summarized as a separate visit, labeled as “Early Study Drug Discontinuation”.
- Data obtained after the follow-up visit or last exposure date (whichever is later) will be excluded from the summaries but will be included in the listings.

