8.1.3. Statistical Analysis Methods

Individual participant concentration data and individual participant PK parameters for VES, VRC07-523LS, and CAP256V2LS will be listed and summarized using descriptive statistics for participants in the corresponding analyte PK analysis set. Summary statistics (number of participants, mean, SD, CV, median, min, max, Q1, and Q3) will be presented for both individual participant concentration data by time point and individual participant PK parameters. For individual participant concentration data for VRC07-523LS and CAP256V2LS, the summaries will only be presented through end of Period 3, since the actual time from study drug dosing varies depending on the time of ART restart for visits after end of Period 3 visit. Moreover, the geometric mean, geometric mean coefficient of variation (GCV), 95% CI for the geometric mean, and the mean and SD of the natural log-transformed values will be presented for individual participant PK parameter data.

Individual concentration data listings and summaries will include all participants with concentration data. If a participant has quantifiable pre-dose, BLQ at end of infusion, or received an incorrect dose, the related PK concentration(s) will be included in the table but will be excluded from the summary statistics, with reasons for exclusion identified. The sample size for each time point will be based on the number of participants with non-missing concentration data at that time point. The number and percentage of participants with concentration BLQ, as well as an indicator if more than one-third of the participants have concentration BLQ, will be presented for each time point. For summary statistics, BLQ values will be treated as zero at baseline and postdose time points. The method to handle BLQ values for PK summaries are described in Section 3.7. Concentration values will be presented as received from the bioanalytical lab and summary statistics will be presented to three significant digits.

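### The by-visit HIV-1 RNA summary in SAP 6.3 has no cut or split at ART restart, so its later rows can pool women back on ART with women still off ART

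*SAP*

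**What the plan says.** SAP 6.3 plans, in the Full Analysis Set, descriptive statistics for log10 HIV-1 RNA change from baseline "at each postbaseline visit up to the last exposure date for participants who have permanently discontinued study drug". The statistics are n, mean, SD, 95% CI, median, quartiles and range; no test is planned. Four other SAP rules fix how that table is built:

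- SAP 3.8.1 on the end point: "Last Exposure Date is defined as last study date for all participants who receive VRC07-523LS and/or CAP256V2LS infusion".
- SAP 3.8.2 on rows: "The nominal visit as recorded on the eCRF or lab date will be used when data are summarized by visit".
- SAP 3.2 places everyone in the Full Analysis Set in the single enrolled regimen.
- SAP 3.4 on splits: "There are no prespecified participant subgroupings for efficacy and safety analyses".

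Protocol Table 6 (Section 6.6) sets one schedule for both parts of Period 4, headed "4A: ART Restart 4B: ATI Extension Days 337 to 413", with visits on Days 343, 357, 371, 385, 399 and 413. Section 6.6.1 takes plasma HIV-1 RNA at each, and Section 6.8 defines one end-of-study visit for completers of either part. SAP 3.8.1 already holds the variable that separates the two states: "ART Restart Date is defined as the start date of resuming ART or compatible regimen after ATI start".

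**The concern.** ART status is the main determinant of plasma HIV-1 RNA. Once some women have restarted and others have not, a pooled row no longer answers one question. Its mean depends on how many women chose or needed ART, and so do its 95% CI and, in places, its median. A reader looking for late viral load off ART could take a diluted figure as evidence of control. At the first Period 4 visit the distortion can go the other way: women who have just restarted because of viremia can produce a pooled rise when every woman still off ART is suppressed.

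**Working it through.** The plan states no figure to reproduce. The check traces the text and then illustrates size.

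**Which rows can mix**

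1. Protocol 6.3.3 requires both antibodies before ATI. Every woman with records after ATI start is therefore an antibody recipient, and her summary limit is her last study date. The table includes Period 4 and the end-of-study visit.
2. Period 4A is on ART and Period 4B is off ART, on the same six nominal days. Women who restart before the end of Period 3 may also enter 4A (Protocol 6.6), and Section 6.6.1 treats the first on-ART visit as Day 343. With one group and no subgroups, nothing in the SAP separates them.
3. The end-of-study visit, 7 days after Day 413 (about Day 420), serves both parts.
4. Mixing is not strictly a Period 4 matter. Protocol 6.9.2 lets a woman who stops study drug and reinitiates ART during ATI stay on the visit schedule. SAP 6.3 also expects to flag women who resumed ART on or before the end-of-Period 3 visit.

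**Illustrative size**

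Document input: results below 20 copies/mL are imputed as 19 (SAP 3.7), and log10(19) = 1.279. Assumptions not in the documents: baseline is 19 for all, women on ART are at 19 (change 0), women off ART share one level, and the off-ART share of the row is 10%, 25% or 50%.

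Pooled mean = off-ART share × off-ART change.

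| Off-ART level (copies/mL) | Off-ART change | 10% off ART | 25% | 50% |
|---|---|---|---|---|
| 200 | 2.301 − 1.279 = +1.02 | +0.10 | +0.26 | +0.51 |
| 1,000 | 3 − 1.279 = +1.72 | +0.17 | +0.43 | +0.86 |
| 10,000 | 4 − 1.279 = +2.72 | +0.27 | +0.68 | +1.36 |

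Reverse case, first Period 4 row: if 4B women are all at 19 and newly restarted 4A women are all at 1,000, the pooled mean is 0.90, 0.75 or 0.50 × 1.721 = +1.55, +1.29 or +0.86, although nobody off ART is viremic.

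Median and interval, with 25 women and an off-ART level of 1,000: with 12 on ART and 13 off, the mean is +0.90 and the median +1.72. With 13 on and 12 off, the mean is 12/25 × 1.721 = +0.83 and the median 0.00. One woman's status moves the median from one extreme to the other. In the second case the SD is 0.878, so a t-based 95% CI is 0.826 ± 2.064 × 0.878/√25 = 0.46 to 1.19. It contains neither 0.00 nor +1.72.

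**The case against.** The strongest reply is that rows follow eCRF visit labels, and the eCRF is not available. Separate labels for 4A and 4B are plausible, because procedures differ between them: dolutegravir sampling and PrEP referral are for 4B only, and the rules for repeat HIV-1 RNA testing differ. Separate labels would keep the six Period 4 rows apart, leaving the end-of-study row (unless it too is labelled separately) and any earlier row containing a woman already back on ART. That stands, and the point is conditional to that extent.

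Second, the table is descriptive and is not among the endpoints in SAP 6.1. It also reports the median and range, and SAP 6.3 adds a by-participant listing and an individual plot. With a small off-ART share, a median of 0 and a high maximum would alert a careful reader. This stands and limits the importance, but it does not make the mean and CI interpretable.

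Third, the sizes are assumed. A woman at 1,000 copies/mL or more for 8 consecutive weeks without a 0.3 log10 drop must restart, and Days 343 to 413 span only 10 weeks. A whole 4B group at 1,000 or above in the late rows is therefore an extreme picture. The 200 copies/mL line does not meet that viral-load rule. Likewise, suppressed women may choose 4A, which weakens the reverse case.

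Fourth, a reader might infer from SAP 8.1.3 that the authors saw this problem and neglected it here. The documents do not support that. There the antibody concentration summaries stop before Period 4, and the reason given is "since the actual time from study drug dosing varies depending on the time of ART restart for visits after end of Period 3 visit"; this concerns time since dosing, not ART status. The section shows only that nominal visits after Period 3 are known not to align across women.

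**Conclusion.** The point holds as a minor one. Followed as written, SAP 6.3 yields rows after ATI start that can combine on-ART and off-ART values, mainly in Period 4 and at end of study. It assumes that women are present in both states at a visit and, for the six Period 4 rows, that the eCRF uses common visit labels. The actual mix is not in the documents, so the +0.17 to +0.86 against a true off-ART +1.72 is an example and not an estimate. A row in which everyone is suppressed is unaffected.

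Three stronger readings are not supported.

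- A reader might infer that the efficacy conclusions are distorted. Time to rebound is censored within ATI, set-point uses individually chosen dates, and time to ART resumption uses the restart itself. These endpoints, the listing, the individual figure and the primary safety endpoints are untouched.
- A reader might infer that the protocol's secondary endpoint of viral load at the end of ATI would be read from these rows. Neither document says so.
- A reader might infer from Protocol 3.3, which allows restart in 4A after 4B, that one woman's off-ART and on-ART values would be averaged under SAP 3.8.3. That would need repeated nominal visits, and the Day 0 anchor in Table 6 and the 60-week maximum fit a single pass.

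**What to change.** In SAP 6.3 and 3.8.2, for every visit after ATI start, classify each HIV-1 RNA record as off or on ART by comparing its sample date with the ART Restart Date in SAP 3.8.1, and state the rule for a sample taken on that date. Summarise off-ART records by study visit and on-ART records separately by weeks since ART restart, with n in every row. Add a footnote that the off-ART rows describe only women who have not yet restarted, so a falling n is part of the result. Applying the rule from ATI start, and not only in Period 4, also covers women who resume early.

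If the SAP is already final, document the split in the CSR, as SAP Section 1 provides. The cost is one descriptive table divided by a date the SAP already derives: no new data, no added visits and no protocol amendment.

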6.8. End-of-Study Visit

The end-of-study visit will occur for participants who have completed Period 4A or 4B. The visit will occur 1 week after completion of the last Period 4 visit. For the purpose of scheduling the end-of-study visit, a \pm 3 day window may be used based on the Day 0 visit + the number of postponement days required to confirm ATI eligibility in Period 1, if applicable.

The ART reinitiation after the end-of-study visit will be up to the participant's health care provider discretion.

The following assessments will be performed at the end-of-study visit:

- Symptom-directed physical examination
- Vital signs (blood pressure, pulse, respiration rate, oxygen saturation, and temperature)
- Body weight
- Review of AEs and changes in concomitant medications
- 12-lead ECG
- Obtain urine collection for:
 - Urinalysis
 - Urine pregnancy testing; a positive result will be confirmed with a serum pregnancy test
- Obtain blood samples for:
 - Plasma HIV-1 RNA
 - Plasma HIV-1 resistance testing (in case of viral rebound) to VRC07-523LS, CAP256V2LS, and baseline ART
 - Chemistry profile: ALP, AST, ALT, total bilirubin, direct and indirect bilirubin, total protein, albumin, CK, bicarbonate, BUN, calcium, chloride, creatinine, glucose, phosphorus, magnesium, potassium, sodium, uric acid
 - Hematology profile: CBC with differential and platelet count
 - CD4+ and CD8+ T cell absolute count, percentage, and CD4/CD8 ratio
 - Creatinine clearance according to the Cockcroft-Gault formula:
$$\text{Female Estimated Creatinine Clearance} = [(140 - \text{age in years}) \times (\text{weight in kg})]/72 \times (\text{serum creatinine in mg/dL}) \times 0.85$$
- The following additional ATI remission tests will be required:
 - HIV-specific antibody profiling using plasma
 - Whole blood ISG mRNA panel
 - Soluble proteins (cytokines, chemokines, and inflammatory markers)
 - PBMC sample for testing of viral sensitivity to the VRC07-523LS and CAP256V2LS mAbs
 - PBMC sample for immune cell frequency, activation, and phenotyping
 - PBMC sample for HIV-specific T cell responses

- PBMC sample for latent HIV-1 reservoir
- PBMC sample for active HIV-1 reservoir
- Plasma sample for active HIV-1 reservoir
- From participants who provide additional consent, lymph node and/or GALT (GALT obtained by rectosigmoid biopsy) tissue collection (within window of \pm 5 days) for some or all of the following tests:

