7.3.2. Adverse Events

Following initiation of study medication, collect all AEs, regardless of cause or relationship, until the end-of-study visit, after completion of Period 4, on the eCRFs as instructed. In case of early discontinuation or early transition from Periods 2 or 3 to Period 4, all AEs, regardless of cause or relationship, must be collected until 250 days after last dose of study drug.

All AEs should be followed until resolution or until the AE is stable, if possible. Gilead may request that certain AEs be followed beyond the protocol-defined follow-up period.

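### Time to ART resumption is censored at a date that can be an AE end date, later than the last review of ART use, so ART-free time may be overstated

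*SAP*

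**What the plan says.** SAP 6.3 analyses time to ART resumption by Kaplan-Meier and gives the censoring rule: "Participants who do not resume ART will be censored at the last study date". SAP 3.8.1 defines the date used: "Last Study Date is the latest clinic visit date, and/or the laboratory visit dates, and/or latest AE onset date and end date, whichever is latest". The event comes from a different form: "ART Restart Date is defined as the start date of resuming ART or compatible regimen after ATI start on Non-Study ARV Medication eCRF form".

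AE follow-up can outlast the visit schedule. Protocol 7.3.2 says: "All AEs should be followed until resolution or until the AE is stable, if possible", and adds: "Gilead may request that certain AEs be followed beyond the protocol-defined follow-up period". ART use after the last visit is outside protocol control. Protocol 6.8 says: "The ART reinitiation after the end-of-study visit will be up to the participant's health care provider discretion". SAP 7.4.1 lists antiretrovirals taken after the study among the recorded data, but only where they were collected.

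The other time-to-event endpoint in SAP 6.3, virologic rebound, has a different rule: "Participants who do not rebound will be censored at the last HIV-1 RNA collection date during ATI period".

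**The concern.** A censoring date should be the last date on which the participant was known to be free of the event. For rebound the SAP does this, because the date is the last measurement of the endpoint itself. For ART resumption the SAP says the analysis follows the same fashion, then takes a general study date that an AE form can set.

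The end date of an AE does not show that the participant was still off ART. Someone off ART at the last visit with an AE still open is credited as event-free until that AE ends. If the participant's own provider restarted ART in between and this was not recorded, the credited time is too long. With at most 25 participants, individual ART-free durations and the tail of the curve will be read closely.

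**Working it through.** **Inputs**
- Time formula (SAP 6.3): (event or censoring date − ATI start date + 1)/7, in weeks.
- ATI start: Day 35 nominal (Protocol 6.4).
- End of Period 3: Day 336. Last Period 4 visit: Day 413. End-of-study visit: 1 week later, Day 420, within ±3 days (Protocol 6.6 and 6.8).
- No document gives the time from last visit to AE end date, so all such gaps below are assumptions.

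**The plan's own figure.** Protocol 3.4 gives a maximum of 43 weeks of ATI to the end of Period 3. The formula gives (336 − 35 + 1)/7 = 43.1 weeks, or 43.0 if ATI starts on Day 36. The figure is reproduced.

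**Period 4B completers.** Censored at the end-of-study visit: (420 − 35 + 1)/7 = 55.1 weeks (54.7 to 55.6 within the window). Under the SAP rule, with an AE ending after that visit:

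| Assumed gap (weeks) | Credited ART-free time (weeks) | Gap / 55.1 |
|---|---|---|
| 2 | 57.1 | 3.6% |
| 4 | 59.1 | 7.3% |
| 8 | 63.1 | 14.5% |
| 12 | 67.1 | 21.8% |

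**Effect on the Kaplan-Meier curve (assumed data).** Suppose 20 participants start ATI. Fourteen resume ART at even spacing from week 8 to week 43.1 (every 2.7 weeks), 4 complete Period 4B at week 55.1, and 2 leave early, last seen at week 16.

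1. *Censored when last seen.* Three events occur before week 16, giving 17/20. The leavers drop out, 15 remain at risk, and 11 more events leave 4. The week-43 estimate is 17/20 × 4/15 = 0.227; the median is 32.3 weeks.
2. *Completers censored 4, 8 or 12 weeks later.* All are still at risk at the last event, so the curve to week 55 stays at 0.227 and the median at 32.3. Only the flat tail, its number at risk and the individual durations lengthen.
3. *Leavers censored later.* The risk set at intervening events grows:
   - 4 weeks: 15/20 × 4/13 = 0.231
   - 8 weeks: 14/20 × 4/12 = 0.233
   - 12 weeks: 12/20 × 4/10 = 0.240
   - 27 weeks: 7/20 × 4/5 = 0.280

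   The median stays at 32.3 weeks.
4. *Both leavers in truth restarted at week 18, unrecorded.* The true week-43 value is 4/20 = 0.200, with a median of 26.9 weeks.
5. *Two of the 4 completers restarted at week 57, unrecorded, and are carried to week 67.* The curve shows 0.227 at week 57; the true value is 0.227 × 2/4 = 0.113.

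Items 4 and 5 show when credited time is wrong rather than only unverified: a restart must fall in the gap and be missed.

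**The case against.** A reader might infer that the rule does overstate ART-free time, and does so for the participants who control the virus. The documents do not support that, for these reasons.

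- A participant who never restarted ART really was ART-free through the AE end date. The extra time is wrong only if a restart occurred and was missed.
- A late restart may be captured. SAP 7.4.1 allows for post-study antiretrovirals, and any recorded restart after ATI start becomes an event. Protocol Appendix 2b pairs AE review with review of medication changes in every follow-up group, so a contact that updates an AE may also inform on ART.
- The trigger is narrow. For participants who complete Period 4, AEs are collected until the end-of-study visit, so a new AE should not extend the date. It needs an AE still open at about Day 420, 42 weeks after the last vesatolimod dose on Day 126, with an end date then entered. An AE followed only until stable need not have one.
- Participants without a restart are not the same as controllers. Suppressed participants may choose ART in Period 4A, restart may be at the participant's request, and viremia below the restart criteria is compatible with staying off ART. Control is better read from the rebound endpoint, whose censoring is sound.
- No test is affected (SAP 3.5).

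All of this stands, and it limits the point to a possibility of modest size. It does not remove it. No passage requires ART status to be confirmed up to the AE end date, and post-study collection is conditional. The exclusion of late data in SAP 3.8.2 gives no cap either: it runs to the later of the follow-up visit and Last Exposure Date, which for antibody recipients is the Last Study Date itself.

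**Conclusion.** The point holds as a possible bias of low severity in a secondary, descriptive endpoint. The SAP can credit ART-free time beyond the last review of ART use, and that time is overstated only if a restart falls in the gap and goes unrecorded.

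For Period 4B completers, later censoring by itself changes only the tail, the late number at risk and individual durations: 55.1 weeks at nominal Day 420, plus whatever gap occurs. The 2- to 12-week gaps and their 3.6% to 21.8% are illustrations, not estimates. For early leavers, later censoring can also enlarge the risk set and slightly raise later estimates (0.227 to between 0.231 and 0.280 in the assumed example). The documents show neither how many participants would be affected nor that any would be.

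**What to change.** In SAP 6.3, replace the censoring sentence for this endpoint. Participants who do not resume ART are censored at the last clinic visit or follow-up contact at which antiretroviral or concomitant medication use was reviewed, no later than the end-of-study or end-of-follow-up visit; AE onset and end dates are not used. This brings the rule into line with the one for rebound. Keep Last Study Date for the safety definitions that depend on it (Last Exposure Date and the treatment-emergent period).

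The cost is one SAP sentence. The documents do not show a separate date for the medication review, but the visit and contact dates can stand for it, because the schedules pair AE and medication review at those contacts. Censored ART-free durations may become slightly shorter. The change does not recover a restart missed after a participant leaves: with both leavers restarting at week 18 in the example, the estimate would still be 0.227 against a true 0.200. It only stops the plan from adding unobserved time on top.
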